3. STATISTICAL BASIS FOR SAMPLE SIZE

With a sample size of 15 patients per group and assuming a standard deviation (SD) of 25 milliequivalent (mEq)/24 hours in change from average Baseline in 24-hour sodium excretion, the study will have 80% power to detect an increase of at least 20 mEq/24 hours in average change from average Baseline 24-hour sodium excretion with dapagliflozin within each group at a two-sided alpha level of 0.05.

Under these same conventions for the number of patients, the SD and the alpha level, and assuming 50% power, the minimum detectable difference in change from average Baseline in 24-hour sodium excretion is approximately 13.6 mEq/24 hours.

Similarly, under the same conventions for the number of patients and the alpha level, 50% power and fixing the change from average Baseline in 24-hour sodium excretion to 20 mEq/24 hours, the maximum SD at which statistical significance can be demonstrated is approximately 37 mEq/24 hours.

It is assumed that approximately 10% of the enrolled patients will not provide evaluable data with regards to the primary endpoint, leading to 17 patients to be enrolled in each of the groups. If the non-evaluable rate is higher than expected, additional patients might be enrolled in order to ensure 15 evaluable patients.

4. RANDOMISATION

Randomisation will not be applied in this study. Patients will be enrolled to specific groups based on their diagnosis. When 17 patients have been enrolled to each specific patient group enrolment into that group will stop, and the evaluability of the data evaluated. If less than 15 evaluable patients in a particular group are found, the recruitment into that group might resume. All patients will receive dapagliflozin 10 mg tablets once daily for 14 days.

5. STATISTICAL ANALYSIS CONVENTIONS

5.1 Analysis variables

5.1.1 Demographic and baseline variables

During the screening visit, baseline patient characteristics (e.g. age, gender and race) will be collected. Relevant medical and surgical history will be recorded, as well as details of T2DM (for T2DM patients) and renal impairment (for patients with impaired renal function). Vital signs, such as pulse and blood pressure, will also be registered. For a detailed list of baseline assessments, please see Appendix A.

5.1.2 Prior and concomitant medication

Any medications administered other than dapagliflozin or indocyanine green (ICG) will be classified as prior or concomitant. The following definitions of prior and concomitant medications will be used:

- **Prior medication**: medications that have been taken prior to first dapagliflozin dose and which have a stop date which indicates that the medication has been stopped before first dapagliflozin are considered prior medication.
- Concomitant medication: medications with a start date on or after first dapagliflozin dose are considered concomitant medications. In addition, medications with a start date of administration prior to the date of first dapagliflozin administration, but which have an end date (or are ongoing) on or after first dapagliflozin administration will be considered as both concomitant and prior medication.

5.1.3 Safety variables

5.1.3.1 Adverse events

AEs and Serious AEs (SAEs), are defined in Section 6.2.1 of the CSP. SAEs will be collected from the time of informed consent until the end of the Follow-up period. All other AEs will be recorded from first dose until the end of the Follow-up period.

5.1.3.2 Clinical laboratory tests

Clinical laboratory tests for safety and eligibility evaluation will be performed pre-dose and during the study (refer to Table 5 and Table 6 study plan for schedule of assessments on the Clinical Study Protocol).

The following variables will be measured:

Lab	Screening	Baseline	ST	ET	FU	
Clinical chemistry	Clinical chemistry					
Creatinine	X	X	X	X	x	
Glucose	X	X	X	X	x	
Total bilirubin	x			x		
AST	x			x		
ALT	X			X		
ALP	X			X		
Haematology (a)						
Haemoglobin	X	X		X		
Haematocrit	x	X	X	x	X	
HbA1C (b)	x					
Urinalysis						
UACR (b)	X					
Dipstick (c)	X			X		
Other	Other					
Pregnancy test	X			X		

⁽a) Note that haematocrit, glucose and creatinine will also be analysed as efficacy endpoints. If the urine pregnancy test is positive, then a serum pregnancy test will also be performed

5.1.3.3 Vital signs

The following measurements will be performed at each time-point:

- Blood pressure (systolic and diastolic, measured in millimetres of mercury [mmHg])
- Pulse rate (measured in beats per minute)
- Weight (kg)

5.1.3.4 12-lead safety electrocardiogram

A 12-lead electrocardiogram (ECG) will be obtained at Screening.

The Investigator will provide an overall interpretation of the ECG as normal, abnormal or borderline and the result will be recorded in the eCRF. If abnormal, the clinical significance

⁽b) For evaluation of the inclusion / exclusion criteria

⁽c) Tests performed are U-albumin, U-glucose and U-blood

(clinically significant or not clinically significant), and the details of the abnormality, will also be recorded in the eCRF.

5.1.3.5 Physical examination

Documentation (yes/no) that the examination was performed will be entered in the eCRF. Any new or aggravated clinically relevant abnormal medical finding at a physical examination as compared with the baseline assessment will be reported as an AE.

5.1.4 Pharmacokinetic variables

There will be no pharmacokinetic parameters derived. A population pharmacokinetic analysis of data may be performed as outlined in a separate population pharmacokinetic analysis plan and the results of this will be reported outside of the CSR and will not be further discussed in this SAP.

5.1.5 Efficacy variables

The full list of measurements performed during the study that are used to evaluate efficacy can be found in Appendix B .

5.1.5.1 Primary Efficacy Endpoint

[figure not shown]
Average change in 24-hr sodium excretion from average Baseline to average values at Day 2 to 4 within each study group.

[figure not shown]
5.1.5.2 Secondary Efficacy Endpoints

The secondary endpoints to be evaluated during or following dapagliflozin treatment within each study group are:

- Average change in 24-hr sodium excretion from average Baseline values to average end of treatment values (Day 12 to 14); and from average end of treatment values (Day 12 to 14) to average values during Follow-up (Day 15 to 17).
- Average change in 24-hr glucose excretion from average Baseline values to average values at Day 2 to 4; from average Baseline values to average end of treatment values (Day 12 to 14); and from average end of treatment values (Day 12 to 14) to average values during Follow-up (Day 15 to 17).
- Change in mean 24-hr systolic blood pressure from Baseline to Day 4; from Baseline to end of treatment (Day 13); and from end of treatment (Day 13) to end of Follow-up (Day 18).
- Change in plasma volume from Baseline to Day 4; from Baseline to end of treatment (Day 14); and from end of treatment (Day 14) to end of Follow-up (Day 18).

- Change in extracellular volume from Baseline to Day 4; from Baseline to end of treatment (Day 14); and from end of treatment (Day 14) to end of Follow-up (Day 18).
- Dapagliflozin pharmacokinetics on Days 4 and 14.
- Average change in mean 24-hr UACR from average Baseline to Day 4; and from average Baseline values to average end of treatment values (Day 12 to 14).

5.2 Analysis sets

5.2.1 Enrolled Set

All patients who provided informed consent will be included in the Enrolled Set.

5.2.2 Run-in Set

All patients who received standard food boxes will be included in the Run-in Set.

5.2.3 Medication Dispensed Set

All patients who were dispensed at least one dose of study drug will be included in the Medication Dispensed Set.

5.2.4 Evaluable Subjects Data Set

This will be a subset of the Medication Dispensed Set. It will exclude primary efficacy variable data which may have been affected by protocol deviations as determined by the medical monitor or agreed by the study team. All decisions to exclude data from the Evaluable Subjects Data Set will be made prior to the database lock of the study during the Data Review Meeting (DRM).

5.2.5 Pharmacokinetic analysis set

The Pharmacokinetic (PK) analysis set will consist of all subjects in the medication dispensed set for whom at least one of the plasma concentration samples are available and who have no important protocol deviations judged to impact the analysis of the PK data.

5.2.6 Safety Set

All patients who took at least one dose of study drug and who have data from at least one post-dose safety assessment available will be included in the Safety Set.

5.3 Statistical analysis methods, general principles

Statistical evaluation will be performed by PAREXEL. Analysis Data will adhere to CDISC (Clinical Data Interchange Standards Consortium) guidance documents for Analysis Data Model (ADaM) and follow their AZ interpretation.

The term "by group" will refer to the grouping of summary data based on the groups as defined in Section 2 in all cases, unless otherwise specified:

- Group 1: T2DM patients with impaired renal function;
- Group 2: T2DM patients with preserved renal function;
- Group 3: Non-diabetic patients with impaired renal function.

In case of a pre-mature termination of the study, or a request of a report of the current results while the study is on-going, all the analyses will be performed on the data available. If there are no patients in one of the groups above, the group will be omitted from all the presentations.

5.3.1 Listings and descriptive statistics

Data will be summarised using descriptive statistics.

For each qualitative variable, frequency counts (number of patients [n] and percentages) will be made. The percentages will be calculated with respect to number of patients in each group. For continuous variables, descriptive statistics will include n, arithmetic mean, standard deviation (SD), median, minimum and maximum, and might include the first and the third quartile. Geometric coefficient of variation (geometric CV%), geometric mean and geometric SD will also be presented in the descriptive statistics for the PK concentration data.

General rounding rules will be followed with regard to the number of decimal places and presentation of data in the tables and listings unless it is deemed scientifically appropriate to display the data in a different format (see Appendix C).

5.3.2 Handling of repeat and unscheduled measurements

All repeated and unscheduled measurements will be presented in the listings. The following general rules will apply to all repeated and unscheduled measurements:

- For repeated measurements obtained prior to the first dose of dapagliflozin the latest value (which may be scheduled or unscheduled) will be used in the calculation of descriptive statistics
- For repeated measurements obtained at the designated Baseline visit, the latest value (which may be scheduled or unscheduled) will be defined as the Baseline provided that this occurred prior to the first dose of dapagliflozin. Repeated measurements designated Baseline will be used in descriptive statistics rather than the planned measurement they replace
- For repeated measurements obtained at any time point after the first dose of dapagliflozin, the first value of any repeated measurements will be used in the calculation of changes from Baseline and for the descriptive statistics. Unscheduled and repeated measurements will not be included in the descriptive statistics at time points after the first dose of dapagliflozin.

5.3.3 Statistical significance level

All statistical tests will be two-sided and will be performed at the 5% level of significance. No multiplicity adjustments will apply. However, it is acknowledged that the issue of false positives is very relevant in this study, as the number of tested hypotheses is large. This issue

will be taken into consideration when interpreting the results, keeping in mind both the expected number of false positives (i.e. rejections of a hypothesis when no effect is in fact present) and clinical feasibility of the pattern of seemingly detected effects.

5.3.4 Software

All statistical analyses and production of tables, figures and appendices will be performed using SAS software version 9.3 or later.

5.3.5 Missing and censored data

In general, missing data will not be imputed. The only exceptions to this rule are missing dates for start or stop of an adverse event, missing dates of start and end of concomitant medications and missing dates for onset of a historical medical condition. For details on imputation rules regarding dates, see Appendix D.

5.3.6 Laboratory data reported above or below a threshold

Any laboratory variables with results from the laboratory given as '<xx', '>xx', '<xx' or '>xx' in the database will be imputed with the absolute value of the number without the sign (e.g., < 2.2 will be imputed as 2.2) for the descriptive statistics, changes from baseline and derivation of any derived variables dependent on this value. Graphical displays will also make use of this convention. Observed value results will be listed as is without any imputation.

5.3.7 Center pooling strategy

It is planned to recruit subjects in different centers. The data from different sites will be pooled for all analyses.

5.3.8 Coding dictionaries

All AEs and medical history will be coded for analysis according to the Medical Dictionary for Regulatory Activities (MedDRA)® coding dictionary, using the latest version available. Prior and concomitant medication will be coded according to the World Health Organisation Drug Dictionary Enhanced + Herbal Dictionary March 2017. Medical procedures will not be coded.

5.3.9 Study population characteristics

5.3.9.1 Patient disposition

An overall disposition will be listed and summarised descriptively, with the descriptive summary done per group and organized by population type (e.g. patients enrolled into study).

All disposition summary tables will be based on the Enrolled Set and the percentages will be based on the number of patients in the Medication Dispensed Set. No percentages will be presented for the number of patients enrolled or for the number of patients in the Run-in Set.

5.3.9.2 Protocol deviations

Protocol deviations will be handled in accordance with PAREXEL SOPs.

Deviations from the protocol will be assessed as "not important" or "important". Important deviations from the protocol may lead to the exclusion of patients from the Evaluable Patients Set and include the following:

- Violation of inclusion and/or exclusion criteria;
- Dosing deviations (e.g., non-compliance);
- Patients receiving prohibited concomitant medications;
- Other procedural and study conduct deviations recorded by the clinical unit on the protocol deviation log.

Compliance will be calculated as specified in Section 5.3.14. Patients will be considered non-compliant for a given interval(s) if the compliance is more than 120% or less than 80%.

Only important protocol deviations (as agreed and documented at the DRM prior to database hardlock) will be reported in the relevant table and listing.

The complete set of criteria for the assessment and reporting of protocol deviations will be stipulated in a separate study-specific protocol deviation specification document.

All important protocol deviations will be listed and summarised by group based on the Medication Dispensed Set. Percentages for the summary will be based on the number of patients in the Medication Dispensed Set for each study group respectively.

Patients and data excluded from the Evaluable Subjects Set will be listed, including the reasons for exclusions. These listings will be based on the Medication Dispensed Set.

5.3.10 Demographics, medical history and baseline data

Demographics (including Screening height, weight, age, gender, ethnicity and race) will be listed by patient based on the Safety Set. Demographic characteristics (age, gender, race, and ethnicity) and patient characteristics (Screening height and weight) will be also summarised based on the Safety Set, by group. The denominator for the percentages will be the number of patients in the Safety Set for each group.

Medical history data will be listed by patient, based on the Safety Set and summarised by group, system organ class (SOC) and preferred term (PT) based on the Safety Set.

Percentages for the summary will be based on the number of patients in the Safety Set for each study group respectively. Surgical history will be listed by patient, based on the Safety Set, showing the procedure and the date of the procedure.

The following additional listings will be presented, based on the Safety Set:

- For patients with T2DM:
 - the date of first diagnosis
 - duration of T2DM
- For patients with renal impairment:
 - date of first diagnosis
 - duration of renal impairment
 - most likely aetiology as detailed in Appendix A.
 - if applicable, chronic glomerulonephritis type as detailed in Appendix A.

The disease duration will be calculated as follows:

• (1 + informed consent date - diagnosis date) / 365.25.

See Appendix D for details the handling of missing or incomplete diagnosis dates.

The following additional baseline characteristics will be summarised, where applicable:

- Duration of T2DM and duration of renal impairment, summarised by:
 - Continuous summary (years)
 - Categorical summary (years): n (%): $< 3, \ge 3 \le 10, > 10$
- HbA1c
 - Continuous summary (%)
 - Categorical summary (%): n (%): $<6, \ge 6 <6.5, \ge 6.5 <7, \ge 7 <8, \ge 8 <9, \ge 9 <10$
- eGFR (mL/min/1.73 m^2)
 - Continuous summary
 - Categorical summary: n (%): $< 30, \ge 30 <45, \ge 45 <60, \ge 60 <90, \ge 90$
- UACR (mg/g)
 - Continuous summary
 - Categorical summary: n (%): $< 30, \ge 30 \le 300, > 300 < 2200, \ge 2200$
- Fasting insulin (uU/ml), continuous summary

5.3.11 Pregnancy testing

Pregnancy testing results will be listed for each female patient, based on the Safety Set.

5.3.12 Prior and concomitant medication

Missing dates/times for prior/concomitant medications will be handled as described in Appendix D.

Prior and concomitant medication will be listed by patient based on the Safety Set (a flag for Evaluable Subjects will be included). The listing will include the information detailed in collected in the eCRF as well as the preferred term, anatomical therapeutic chemical class and classification as prior or concomitant (or both where applicable).

Prior and concomitant medications will be summarised by group, separately for prior and concomitant medications, based on the Safety Set. Percentages will be based on the number of patients in the Safety Set for each group.

5.3.13 Exposure to investigational product

Exposure to dapagliflozin will be listed for each patient, based on the Safety Set. The date and time (where available) of administration, as well as the duration of exposure will be included in the listing.

Duration of exposure is defined as the number of days exposed to study drug and calculated as (last dosing date - first dosing date) + 1.

The duration of exposure will be summarised by descriptive statistics.

5.3.14 Compliance to investigational product

Compliance will be calculated and expressed as a percentage. Based on the tablet counts, the percentage treatment compliance will be calculated as the number of tablets taken (dispensed minus returned) relative to expected number of taken tablets:

• 100 x (number of tables taken / expected number of taken tablets)

The expected number of tablets taken will be calculated as:

• (number of tablets taken daily) × (number of days between visits, until treatment is completed or permanently discontinued).

The following intervals will be considered for the calculation of compliance:

- Overall: based on Day 1 to Day 14; this will only be calculated for patients completing the treatment period (Day 1 Day 14);
- Start of Treatment: based on Day 1 to Day 4;
- Maintenance Treatment: based on Day 5 to Day 11;
- End of Treatment: based on Day 12 to Day 14.

Based on drug accountability obtained from the eCRF, the compliance for the overall period will be tabulated. The compliance will also be listed by patient including results for both drug accountability obtained from eCRF and patient diaries. The safety set will be used.

5.3.15 Food and fluid consumption

Details regarding food and fluid consumption will be listed by patient based on Safety Set.

5.3.16 Efficacy analysis and reporting, general approach

Unless otherwise specified, all listings and individual patient figures in this section will be based on the Evaluable Subjects Set; all tables and mean figures in this section will be based on the Evaluable Subjects Set.

5.3.16.1 Statistical models

For each efficacy variable, and each patient group, two models will be constructed. The first will be used to estimate the change from baseline to ST, and from baseline to ET. The second will be used to estimate the change from end of treatment to follow-up.

Model 1

Due to the likely dependence between within-patient observations, the first model will be a linear mixed effect model with time (ST and ET), the baseline value of the variable and the interaction between the two as fixed effects. The within-patient dependence is incorporated through covariance matrix of the residuals, which is assumed to be unstructured. Least squares mean (LSM) estimates of average effect at each one of the two time points will be obtained from the model and tabulated, together with the 95% confidence intervals (CI) and p-values.

Kenward-Rogers method will be used for approximation of degrees of freedom for the tests from which the p-values are obtained.

Explicitly, the following SAS code will be used for the first model:

```
PROC MIXED DATA = <DATA>;
BY <GROUP>;
CLASS <TIME> <USUBJID>;
MODEL <CHANGE> = <TIME> <BASE> <TIME> * <BASE> / DDFM =
KENWARDROGER;
REPEATED <TIME> / TYPE = UN SUBJECT = <USUBJID>;
LSMEANS <TIME> / CL ALPHA = 0.05;
RUN:
```

where <GROUP> is the variable representing the patient group, <CHANGE> refers to the variable containing the change versus the baseline for each patient, <TIME> refers to the

time-point, <USUBJID> refers to the variable containing the patient numbers, <BASE> refers to the baseline value; <TIME> * <BASE> refers to the interaction term.

In case on non-convergence of the model the following alternative will be explored in order, as required:

Each of the groups and each of the timepoints will be considered separately by fitting a linear regression model with change between baseline to the specific timepoint (ST, ET) as the response and the baseline value of the modelled endpoint as a single covariate. Similarly, to the original model, the estimated expected change from baseline for a patient with an average baseline value (which can be seen as a form of LSM), as well as the 95% CI and p-value, will be tabulated.

Explicitly, the following SAS code will be used:

```
PROC MIXED DATA = <DATA>;
BY <GROUP> <TIME>;
CLASS <GROUP>;
MODEL <CHANGE> = <BASE> <GROUP>;
LSMEANS <GROUP>/ CL ALPHA = 0.05;
RUN;
```

With variable names as above.

Model 2

The model for the change between the ET and the FU timepoints will be a linear regression model. This model will be constructed for each group separately and include the baseline value of the studied endpoint as a single covariate. Similarly, to the back-up option for Model 1, the estimated expected change between ET and FU for a patient with an average baseline value, as well as the 95% CI and p-value, will be tabulated.

This will be done using the following SAS code:

```
PROC MIXED DATA = <DATA>;
BY <GROUP>;
CLASS <GROUP>;
MODEL <CHANGE> = <BASE> <GROUP>;
LSMEANS <GROUP> / CL ALPHA = 0.05;
RUN;
```

Here, <CHANGE> refers to the change between ET and FU.

The approach described above will be applied for the analyses of all endpoints, with the exception of PK (discussed separately in Section 5.3.16.5).

The formal analyses will be accompanied by listings, tables with summary statistics and Box plots. The summary tables for the values observed at each measurement timepoint will be presented for each group separately, in general including mean n, SD, median, minimum, maximum, as well as the first and third quartiles. For the change from baseline, the summary will include n, median, minimum and maximum.

5.3.16.2 24-hour urine data

A listing of urine sample collection, showing each collection day's start and stop date/time, urine sodium amount excreted, urine glucose concentration, urine glucose amount excreted, urine volume and UACR, will be presented.

A separate listing will be presented showing the by-patient arithmetic mean of the urine sodium amount excreted, urine glucose amounts excreted urine volume and UACR taken across the following summary periods:

- Baseline: Day -3 up to and including Day -1;
- Start of Treatment (ST): Day 2 up to and including Day 4 and for UACR ST: Day4;
- End of Treatment (ET): Day 12 up to and including Day 14;
- Follow-up (FU): Day 15 up to and including Day 17.

The following by-patient changes will be derived for each urine sodium amount excreted, urine glucose amount excreted, urine volume and UACR:

- ST average versus the BL average
- ET average versus the BL average;
- FU average versus the ET average.

Changes in urine sodium amount excreted, urine glucose amount excreted, urine volume and UACR will be listed, for each of the change types specified above.

Each of the average summary periods (Baseline, ST, ET and FU), as well as the individual study day values, will be summarised for urine sodium amount excreted, urine glucose amount excreted, urine volume and UACR, by group.

Calculated by-patient changes, for each of the change types defined above (i.e., each of the defined intervals/days where changes are calculated), will be summarised by group and time-point.

Box-plots for each change type versus time-point will be presented, with all groups overlaid on the same plot and separate plots for each of urine sodium amount excreted, urine glucose amount excreted, urine volume and UACR.

5.3.16.3 24-hour blood pressure monitoring

The results of systolic and diastolic blood pressure will be listed for each of the intervals over which this is collected over the 24-hour period.

The following by-patient averages will be derived and listed for systolic and diastolic blood pressure, for each of the collection days as specified in Section 5.1.5.3:

• Daily average defined as the average over the entire 24 hours collection;

The following rules will apply with regards to incomplete blood pressure measurements:

• Daily average: a minimum of 40 valid data points will be required for the calculation of the daily average; otherwise, no Daily average will be calculated.

The above rules are based on the following sampling frequencies and the requirement that 50% of data be non-missing:

- a sampling frequency of every 15 minutes (= 0.25 hours) during the day, which would result in $\sim 16/0.25 = 64$ data points over a 16 hour period is time-period;
- a sampling frequency of every 30 minutes (= 0.5 hours) during the night, which would result in $\sim 8/0.5 = 16$ data points over an eight hours period;
- 64 + 16 = 80 data points over the whole 24-hour period;

For each patient, **CCI** will be derived and listed for systolic and diastolic blood pressure.

Changes in the daily average CCI will be derived and listed. The following changes will be derived:

- Change from Baseline (Day -1) to ST (Day 4);
- Change from Baseline (Day -1) to ET (Day 13);
- Change from ET (Day 13) to FU (Day 18).

Daily averages, CCI and and the corresponding changes will be summarised by group and time-point.

Boxplots for daily averages, CCI will be presented, with all groups overlaid on the same plot and separate plots for systolic and diastolic blood pressure, CCI.

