8.3.1 Primary Efficacy Analysis

The primary efficacy endpoint is the average change in 24-hr sodium excretion from average Baseline to average values at Day 2 to 4 within each study group. This will be analysed as follows "average change in 24-hr sodium excretion during dapagliflozin treatment between Baseline (average of Days -3 to -1) and average of Days 2 to 4 within each study group".

The primary analysis will be performed separately for each study group using a longitudinal repeated-measures analysis for the "change from average Baseline" as dependent variable, with a term for Baseline value. Point estimates and 95% confidence intervals will be calculated for the adjusted mean changes within each study group.

The primary analysis will be based on the Evaluable Subjects Analysis Set.

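### The baseline-adjusted LS mean in each single-arm Model 1 has a standard error that omits sampling error in the baseline mean, so the primary confidence interval can be too narrow and the 5% test too liberal

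*SAP*

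**What the plan says.** The endpoint (Protocol 3.2.1; SAP 5.1.5.1) is the group's average change in 24-hour sodium excretion from baseline to Days 2 to 4. There is no randomisation and no comparator. Protocol 8.3.1 analyses each group separately with a baseline term: "Point estimates and 95% confidence intervals will be calculated for the adjusted mean changes within each study group".

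SAP 5.3.16.1 implements this as Model 1, a "linear mixed effect model with time (ST and ET), the baseline value of the variable and the interaction between the two as fixed effects", run by group with an unstructured residual covariance and Kenward-Roger degrees of freedom. The LSMEANS statement has no AT option, so the LS mean is evaluated at the sample mean baseline. If the model does not converge, a regression of change on baseline is fitted at each time point, and its target is described as "the estimated expected change from baseline for a patient with an average baseline value (which can be seen as a form of LSM").

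SAP 5.3.3 states: "All statistical tests will be two-sided and will be performed at the 5% level of significance". SAP section 3 bases the sample size on the raw change, "assuming a standard deviation (SD) of 25 milliequivalent (mEq)/24 hours in change from average Baseline in 24-hour sodium excretion". On reporting, SAP 5.3.16.1 says: "For the change from baseline, the summary will include n, median, minimum and maximum".

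**The concern.** In a randomised comparison, adjusting for baseline corrects chance imbalance between arms and improves precision. Here there is one arm. The adjustment has nothing to balance, and with complete data it leaves the estimate unchanged. It changes only the standard error, by treating the observed baseline mean as a fixed, known value.

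The endpoint is a change from that same baseline mean, so its chance error passes directly into the estimate. A standard error that leaves this out describes the change at one particular baseline value, not the average change in the population the group represents. At stake are the width of the primary confidence interval and the level of the primary test, and likewise the other changes from baseline analysed by Model 1.

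**Working it through.** **Inputs from the documents.** n = 15 evaluable per group, SD of change 25 mEq/24 h, difference 20 mEq/24 h, 80% power (SAP section 3; Protocol 8.6); two-sided 5% (SAP 5.3.3); the model and code in SAP 5.3.16.1.

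**Inputs the documents do not give.** The baseline/on-treatment correlation ρ, and the ratio k of on-treatment SD to baseline SD. Assumed here: ρ from 0 to 0.9, k = 1 or 1.3, bivariate normality, complete data.

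**1. The plan's own figures.** A one-sample t-test on the change with 14 df has non-centrality 20 × √15 / 25 = 3.098 and power 82.1%; n = 14 gives 79.0%, so 15 is the smallest n reaching 80%. At 50% power the minimum detectable difference is 13.59 (stated 13.6) and the maximum SD is 36.8 (stated 37). Enrolment is 15/0.9 = 16.7, rounded up to 17. All figures reproduce, and all rest on the unadjusted test.

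**2. What Model 1 tests.** A least-squares line passes through the point of means, so the LS mean at the sample mean baseline is the raw mean change D̄. Its model variance is σ²res/n. The actual variance of D̄ is

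Var(D̄) = (σ²res + b²σ²x)/n,

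where b is the slope of change on baseline and σ²x the baseline variance. The term b²σ²x/n is missing. A REML fit of the two-time unstructured model to one complete simulated dataset gave the same LS means and standard errors (4.126 and 4.802) as separate regressions at each time, so the regression result carries over to Model 1.

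**3. How much variance is left out.** The slope is b = kρ − 1, and the share of variance the model keeps is

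q = k²(1 − ρ²) / (1 + k² − 2ρk), which is (1 + ρ)/2 when k = 1.

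**4. Type I error for zero mean change in the population.** The residual SD is independent of D̄, so the test statistic is a t variable on 13 df divided by √q, and the rejection rate is P(|t13| > 2.160 × √q). For ρ = 0 and k = 1 the cut-off is 2.160 × 0.707 = 1.528, giving 15.1%. The expected CI half-width at SD 25 is 2.160 × 25 × √(q/15) × 0.981, where 0.981 is the ratio of expected sample SD to true SD on 13 df.

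| ρ | k = 1: q | type I error | mean half-width, mEq/24 h | k = 1.3: q | type I error |
|---|---|---|---|---|---|
| 0 | 0.500 | 15.1% | 9.7 | 0.628 | 11.1% |
| 0.5 | 0.750 | 8.4% | 11.9 | 0.912 | 6.0% |
| 0.75 | 0.875 | 6.4% | 12.8 | 0.999 | 5.0% |
| 0.8 | 0.900 | 6.1% | 13.0 | 0.997 | 5.0% |
| 0.9 | 0.950 | 5.5% | 13.3 | 0.917 | 5.9% |

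The unadjusted analysis has an expected half-width of 2.145 × 25/√15 × 0.982 = 13.6. Simulation with 200,000 trials per setting agrees: 15.1%, 8.5%, 6.2% and 5.4% at ρ = 0, 0.5, 0.8 and 0.9 with k = 1, against 4.9 to 5.1% for the unadjusted test in every n = 15 setting. Results at n = 17 are almost the same.

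**5. The conditional null.** If the hypothesis is zero change at the observed mean baseline, the planned test rejects in 4.9 to 5.1% of n = 15 trials in every setting.

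**6. Model 2.** Baseline is not a component of the change from end of treatment to follow-up, so the coupling in step 2 is absent. Simulated type I error was between 4.9% and 6.0%.

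**The case against.** The strongest reply is that the target is a choice. The SAP describes the fallback estimate, and by analogy Model 1, as the change for a patient with average baseline, and Protocol 8.3.1 pre-specifies adjusted means. Inference conditional on covariates is ordinary regression practice, and step 5 shows that it holds its level. This stands as a description of the conditional analysis. It does not settle the matter, because the objective and endpoint are the average change within the group, SAP 5.3.16.1 itself presents the LS means as average effects, and the baseline conditioned on is a value that moves from sample to sample.

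It is also fair that ρ = 0 is an extreme case. Both periods are three-day averages, which raises ρ. In a simulation with SD of change 25 and assumed between-patient SDs of 15, 20, 25, 30 and 40, type I error was 9.1%, 7.7%, 6.9%, 6.5% and 5.8%. The fixed 150 mmol diet makes a lower ρ plausible but does not establish it.

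A reader might infer more than the documents support:

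- **A fixed inflation of 6 to 15%.** That range needs equal SDs and ρ between 0.8 and 0. Other values give about 5%, and a negative ρ gives more than 15%.
- **Equal damage to every endpoint.** The size varies with each endpoint's slope, and nothing in the documents sizes it for blood pressure, volumes or UACR.
- **The fix stops a chance low baseline from looking like natriuresis.** With complete data the point estimate is the same either way; only the interval changes. Eligibility selects on stability between Days -3 and -2, not on low excretion.
- **The raw result is hidden.** The LS mean is the raw mean with complete data, by-patient changes are listed and summarised (SAP 5.3.16.2), and SAP 5.3.1 includes mean and SD. What remains is that the specific rule for change in 5.3.16.1 is narrower than that general rule.

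Planning on the raw SD and analysing with a covariate is common and is not an error in itself.

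**Conclusion.** The concern holds for Model 1 and its fallback. For the stated endpoint, the standard error is too small whenever the slope on baseline is non-zero. Under equal SDs and ρ of 0.5 to 0.8, the excess over 5% is about 1 to 3.5 percentage points. It reaches about 10 points at ρ = 0, and it nearly vanishes at high correlation with equal SDs or where the SD ratio brings the slope close to zero. These sizes rest on assumed values of ρ and k, normality and complete data; the direction does not depend on the particular values of ρ and k. The mismatch matters because the sample size was justified by the unadjusted test and SAP 5.3.3 applies no multiplicity adjustment while acknowledging the risk of false positives. Severity: should-fix. The study is small and mechanistic, and the point estimate is unaffected with complete data.

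**What to change.** - **Primary inference and other Model 1 changes from baseline.** Use MODEL CHANGE = TIME with unstructured covariance, Kenward-Roger and LSMEANS TIME. Alternatively, put Baseline, ST and ET in the response vector and estimate the time contrasts. The two agree with complete data; the second keeps baseline information when later values are missing.
- **Fallback for Model 1.** Drop BASE there too.
- **Adjusted model.** Keep it as supportive, labelled as the change at the observed mean baseline. Align the wording in Protocol 8.3.1.
- **Reporting.** Add mean, SD and 95% CI to the change-from-baseline summary in SAP 5.3.16.1, in line with the mean and SD already required by SAP 5.3.1.
- **Model 2.** No change is needed on this ground.

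The cost is a few lines of code and SAP text, and an interval that may be somewhat wider. The stated 80% power is unaffected, since the unadjusted test has 82% at n = 15. What is given up is the higher nominal power of the adjusted test (88% at ρ = 0.5, 84% at ρ = 0.8, equal SDs), which comes from the same understated standard error.
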